#### 9.0 Procedures Involved\*

- 9.1 This is a prospective randomized study of an educational website.
- 9.2 Potential participants will be offered participation in the study. If they choose to participate, they will be enrolled following the consent process. They will be randomized into either control group or intervention group. Control group participants will receive usual care and routine hospital pain-relief information. Intervention group participants will receive usual care, plus one hour in which to view the patient education website thepainlesspush.com, on an iPad provided by the Anesthesiology department for this purpose. After their delivery and transfer to the mother/baby unit, participants will complete a satisfaction survey brought to them by a study team member. Participants will complete the survey following their delivery and prior to discharge. Their active participation in the study will be complete at this time.
- 9.3 After a participant completes the satisfaction survey, research team members will collect demographic information and relevant obstetric/medical history information from the electronic medical record.

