#### 14.0 Risks to Subjects

- 14.1 The only difference between study arms is the availability of an educational website. Therefore, the primary risk relates to potential loss of confidentiality. A reduced dataset of demographic and health-related information will be gathered to better understand patterns in the post-delivery satisfaction survey data. Similarly, identifiers will only be kept temporarily in order to accurately link arm assignment, demographic/health data, and satisfaction survey responses.
- 14.2 The investigators do not believe that the study procedures may reasonably be said to carry substantial unforeseeable risks: the study consists of access to an educational website (or routine information) and a satisfaction survey.
- 14.3 All subjects will be pregnant at the time of enrollment, but the investigators have not identified any risks to the fetus arising from reading an educational website. This project does not propose to modify any clinical decisions made by parturients, physicians, nurses, or midwives. The remaining study procedure, completing a satisfaction survey, occurs after delivery.
- 14.4 The investigators have not identified any risks to others arising from subjects' participation in this study.

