# **16.0** Vulnerable Populations

16.1 The study targets pregnant women, but no other vulnerable group (prisoners, students, economically disadvantaged, etc). Pregnant women are regularly seen for labor and delivery at UNM Hospital. [name] regularly treats laboring women as part of her routine clinical duties. This study does not modify any clinical decisions.

Page 5 of 10 Template: 7/1/2015

As noted elsewhere, the only intervention is the selection of painrelief educational materials: the existing materials in routine use, or the newly-developed website. The study thus presents minimal risk.

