### 19.0 Setting

- 19.1 Research sites/locations:
  - Potential participants will be recruited from the UNMH Labor & Delivery floor. All patients admitted to that unit who are expected to progress to active labor during that admission will be eligible for enrollment.
  - All research procedures will occur at UNMH. Recruitment and patient education (routine or with the website being evaluated) will occur in the Labor & Delivery areas. The post-delivery satisfaction survey will occur in the Mother/Baby Unit. Collection of relevant data from the electronic medical record will occur at UNM HSC via workstations with regular access to the medical record.

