#### **26.0** Consent Process

26.1 Consent will be obtained prior to enrollment. The investigators are requesting waiver of documentation of consent and HIPAA authorization, and use of an oral process for both consent and HIPAA authorization. As noted above, the research presents no more than minimal risk of harm to subjects. Similarly, it is routine to provide information on analgesia options and consultation to laboring women at UNMH. The educational website being evaluated is merely a specific option within the available educational materials. Healthcare satisfaction surveys (such as the Press Ganey healthcare satisfaction survey) are regularly conducted without formal written consent. For those reasons, the investigators believe that this project involves no procedures for which written consent is normally required outside the research context. The demographic and health information to be used in this study will be obtained from the electronic medical record by authorized personnel, and identifiers will be kept only temporarily. A script for an oral consent and

Page 8 of 10 Template: 7/1/2015

HIPAA authorization process is included with this application, along with a post-participation informational handout. The oral consent/HIPAA script includes the usual elements of consent, as well as listing the PHI to be used for the study, referencing HIPAA and the requirement that patients give permission for use of PHI, and specifically asking for permission to "let us use your protected information."

- The consent process will occur in regular patient rooms on the UNMH Labor/Delivery floor, which are already sufficiently private for appropriately confidential doctor/patient conversations.
- The investigators believe that avoiding the requirement for prospective participants to read, comprehend, and sign a complicated consent/HIPAA document while in labor will better respect their privacy considerations. An oral process will be considerably less intrusive, while respecting patient autonomy and addressing all other required elements of consent and HIPAA authorization.
- Patients will be free to read the educational materials, or not, as they see fit; similarly, they can choose to decline to answer any or all of the satisfaction-survey questions. The investigators do not anticipate that ongoing consent will become an issue.

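### Do the differing descriptions of the two arms leave it unclear what the trial compares?

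*Combined protocol and SAP*

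**What the plan says.** Six places in the combined protocol and SAP describe the contrast between the arms.

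- Section 9.2 (Procedures Involved): "Control group participants will receive usual care and routine hospital pain-relief information". For the other arm: "Intervention group participants will receive usual care, plus one hour in which to view the patient education website thepainlesspush.com".
- Section 14.1 (Risks to Subjects): "The only difference between study arms is the availability of an educational website".
- Section 14.2: "the study consists of access to an educational website (or routine information) and a satisfaction survey".
- Section 16.1 (Vulnerable Populations): "the only intervention is the selection of painrelief educational materials: the existing materials in routine use, or the newly-developed website".
- Section 19.1 (Setting): "patient education (routine or with the website being evaluated) will occur".
- Section 26.1 (Consent Process): "The educational website being evaluated is merely a specific option within the available educational materials". The same section says that "it is routine to provide information on analgesia options and consultation to laboring women at UNMH", and that reading the materials is up to the patient.

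The data to be collected or linked appear in 9.3, 11.3, 12.0 and 14.1: survey answers, arm assignment, and demographic and medical-record items. None of the four mentions routine information received or website viewed. The hypothesis in 1.2 is that women with access to the website will be more satisfied. Section 11.1 compares the arms on the survey questions with a Wilcoxon-Mann-Whitney test.

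**The concern.** Taken literally, 14.1 and 16.1 describe different trials. If availability of the website is the only difference, and controls get routine information under 9.2, then the website arm must get routine information too. If the intervention is a choice between existing materials and the website, the arms differ in two respects: one has the website without the routine materials, the other the reverse. Section 9.2 does not close the question, because it names routine information for one arm only. A reader of the results might then not know whether the trial tested adding the website or replacing something with it.

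The second worry is exposure. Viewing is optional, and 7.1 allows that participation may last only hours, so some women offered the site may not look at it. Without a record of viewing, a null result could mean that the site was not seen or that it was seen and did not help. Under 11.4 the linking document is shredded once data collection is complete, so a record could not reliably be rebuilt afterwards.

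**Working it through.** **1. The six descriptions side by side.**

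| Section | Purpose of the section | Reading |
|---|---|---|
| 9.2 | Procedures | Leans to add-on: usual care with the website added |
| 14.1 | Risk | Implies add-on: one difference only |
| 14.2 | Risk | Either/or wording; does not settle it |
| 16.1 | Vulnerable populations | Reads as substitution |
| 19.1 | Setting | Does not settle it; *with the website* also fits add-on |
| 26.1 | Consent | Website is one option among materials; also says analgesia information is routine |

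One of six reads as substitution, two point to add-on, and three do not settle it by themselves. None says outright that the website arm also receives routine information.

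**2. Which text governs.** Section 9.2 tells staff what to do. The sentence in 16.1 opens by referring back to other sections and supports a minimal-risk conclusion. It can be read as saying that the study varies educational materials and not clinical decisions. Section 26.1 supplies the missing link: if analgesia information is routine for laboring women at this hospital, usual care in the website arm would be expected to include it. That makes 9.2 and 14.1 agree. Section 21.3 fits as well, since Anesthesiology is routinely notified of these patients for possible consultation. No section instructs anyone to withhold routine information.

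**3. What each reading does to the analysis.** Write Y for a survey score.

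- Add-on: compare Y under (routine information + website offered) with Y under (routine information).
- Substitution: compare Y under (website offered) with Y under (routine information).

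In both cases the groups are those formed by randomisation, the test is the one in 11.1, and the target is about 100 completed surveys. Only the sentence describing the comparison in the report would differ.

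**4. The plan's only figure.** Sections 4.3 and 11.2 give a detectable difference of about 58% of a standard deviation at 80% power. Assume a two-sided 0.05 level, 50 per arm (1:1 is not stated) and normal-theory Wilcoxon efficiency 3/π = 0.955. The effective size is 50 × 0.955 ≈ 47.7 per arm. The normal approximation gives (1.960 + 0.842) × √(2/47.7) ≈ 0.57; the t-based calculation gives 0.579. The stated figure reproduces. It refers to the difference between randomised arms and is computed the same way under either reading.

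**5. What a viewing record would add.** It would give the proportion of the website arm who looked at the site. It would not alter the by-arm difference or its test, and would not restore power lost to non-viewing. Nor would it show whether the site helps those who view it, because viewers select themselves and comparing them with non-viewers is no longer a randomised comparison.

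**6. Whether the record is missing.** Of the four places that list data, 11.3 explains why identifiers are kept, while 12.0 and 14.1 concern risk and confidentiality. Only 9.3 describes collection, and it covers what is taken from the medical record after the survey. A note of iPad use would not be expected there. The survey and data form, where it would sit, are not in the file.

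**The case for a change.** The strongest case for a change is that if usual care already includes routine information, 9.2 had no reason to name it separately for controls; naming it for one arm invites the inference that the other does without. Sections 14.1 and 16.1 also each use their version of the contrast to support a statement about risk, so the wording carries some weight. The remedy is cheap: a few words, one form line and one survey item, with no extra patients. Section 1.1 sets out to evaluate the website, and a null result is easier to interpret when uptake is known.

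What stands is that the wording is uneven and that add-on is inferred from several sections and stated in none. A descriptive count of viewers would also be useful context. What does not stand is that either point affects the comparison. The hypothesis in 1.2 concerns access, 14.1 stresses availability, and the by-arm analysis estimates the effect of offering access. The shredding in 11.4 adds little, because anything recorded during the study can be linked before the linking document is destroyed.

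**Conclusion.** No change to the plan is called for. The inconsistency is a matter of drafting: one loose summary in 16.1, with similar wording in 14.2, against a procedures section that, read with 14.1 and 26.1, points to the website being added to routine information. Aligning the wording would be harmless editing, and recording who viewed the site is optional. Neither would change the randomised comparison, its test or its sample size.

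No size can be put on the exposure point, because the documents give no viewing rate and no rate of receiving routine information. The conclusion rests on two assumptions: that staff follow 9.2 and do not withhold routine information from the website arm, and that the report describes the result as the effect of offering access. If the first failed, the comparison by arm would still be a valid randomised one, but the report would have to describe it as website in place of routine information.

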#### 17.0 Community-Based Participatory Research

17.1 This project does not involve community-based participatory research.

### 18.0 Sharing of Results with Subjects

18.1 The investigators do not plan to share overall study results with participants. Others' satisfaction is not clearly relevant to participants' birth experience.

### 19.0 Setting

- 19.1 Research sites/locations:
  - Potential participants will be recruited from the UNMH Labor & Delivery floor. All patients admitted to that unit who are expected to progress to active labor during that admission will be eligible for enrollment.
  - All research procedures will occur at UNMH. Recruitment and patient education (routine or with the website being evaluated) will occur in the Labor & Delivery areas. The post-delivery satisfaction survey will occur in the Mother/Baby Unit. Collection of relevant data from the electronic medical record will occur at UNM HSC via workstations with regular access to the medical record.

#### 20.0 Resources Available

- 20.1. PI [name] is a faculty member in the UNM Department of Anesthesiology & Critical Care Medicine, with all relevant licensures and credentials. Investigator [name] is a third-year medical student at the University of New Mexico School of Medicine. She has previous human-subjects experience at UNM SOM and Southwest Women's Health.
- 20.2. All medical decisions will be made by duly authorized and licensed personnel at UNM HSC, with input from participants as appropriate. The existence of this study does not modify any clinical decision.
- 20.3. The necessary resources are available, as noted below:
  - UNMH serves thousands of parturients per year. Only a small percentage of them would need to complete this study for it to achieve its target sample size in less than one year.
  - [name] has regular nonclinical time that is intended for activities such as the planned project. Likewise, the two medical-student investigators are expected to participate in research as part of their curriculum. Adequate time is available.

Page 6 of 10 Template: 7/1/2015

- UNMH has adequate facilities to care for laboring women, and resources are available within the Anesthesiology department to ensure completion of the research, including IRB liaison, study design and statistical support, and manuscript preparation.
- The research consists of an educational opportunity and satisfaction survey. As a result, the investigators do not anticipate any need for medical or psychological resources resulting from consequences of participation.
- The study team is relatively small, and the research is to be conducted in one center. The HRRC-approved version of the protocol will be shared among the investigators prior to study commencement, and study procedures will be reviewed.

#### 21.0 Recruitment Methods

- 21.1 Patients will be recruited following admission to the UNMH Labor & Delivery floor for expected delivery.
- 21.2 UNMH serves a large catchment area, and expectant mothers present daily for labor and delivery.
- 21.3 Physicians on the Obstetrics service routinely notify Anesthesiology of parturients expected to progress to active labor, in order for them to provide possible consultation and appropriate pain relief care. The study team will identify potential participants from among this patient population. Anesthesiology providers regularly review the medical records of this patient population upon receiving this notification, for purposes of clinical treatment. The investigators are requesting a partial waiver of HIPAA authorization requirements in order to permit the use of a subset of these records for purposes of verifying eligibility (i.e. that potential participants do not meet the few exclusion criteria). The research-related protected health information will not be reused or disclosed to any other person or entity, except as required by law, for authorized oversight of the research study, or for other research for which the use or disclosure of protected health information for which an opportunity to agree or object is not required by 45 CFR 164.512.
- 21.4 Recruitment will occur in person, and will not involve audio or video materials.
- 21.5 A recruitment flyer will be posted in patient areas of the Labor & Delivery floor, and copies of it may be distributed to potential participants.
- 21.6 Participants will not be paid.

# 22.0 Number of Subjects

22.1. This is not a multicenter study.

Page 7 of 10 Template: 7/1/2015

- 22.2. The investigators plan to recruit up to 150 patients. The target sample size after attrition is approximately 100 completed surveys, but if actual attrition is less than anticipated, data may be obtained on up to 150 participants.
- 22.3. There is not a screening step between enrollment and determination of eligibility for procedures or data collection.

#### 23.0 Provisions to Protect the Privacy Interests of Subjects

- 23.1 Investigators who will conduct recruitment and consent are already authorized for patient contact in this situation, so recruitment will not involve any extraneous or unexpected personnel.
- 23.2 Investigators are already experienced at interacting with patients during a time that is stressful in general (i.e. labor) and at specific moments during that time (i.e. between contractions). Recruitment and consent efforts will not interfere with these interactions, or be "forced" during contractions.
- 23.3 The PI is already authorized to contact these patients and review their records as part of medical practice.
- 23.4 The post-delivery satisfaction survey will occur in the Mother/Baby Unit prior to discharge, in order to provide some opportunity to recover from the stress of delivery.

#### 24.0 Compensation for Research-Related Injury

24.1 This is a Minimal Risk study.

## 25.0 Economic Burden to Subjects

25.1 Participant costs will not be affected by the availability of these educational materials.

#### **26.0** Consent Process

26.1 Consent will be obtained prior to enrollment. The investigators are requesting waiver of documentation of consent and HIPAA authorization, and use of an oral process for both consent and HIPAA authorization. As noted above, the research presents no more than minimal risk of harm to subjects. Similarly, it is routine to provide information on analgesia options and consultation to laboring women at UNMH. The educational website being evaluated is merely a specific option within the available educational materials. Healthcare satisfaction surveys (such as the Press Ganey healthcare satisfaction survey) are regularly conducted without formal written consent. For those reasons, the investigators believe that this project involves no procedures for which written consent is normally required outside the research context. The demographic and health information to be used in this study will be obtained from the electronic medical record by authorized personnel, and identifiers will be kept only temporarily. A script for an oral consent and

Page 8 of 10 Template: 7/1/2015

HIPAA authorization process is included with this application, along with a post-participation informational handout. The oral consent/HIPAA script includes the usual elements of consent, as well as listing the PHI to be used for the study, referencing HIPAA and the requirement that patients give permission for use of PHI, and specifically asking for permission to "let us use your protected information."

- The consent process will occur in regular patient rooms on the UNMH Labor/Delivery floor, which are already sufficiently private for appropriately confidential doctor/patient conversations.
- The investigators believe that avoiding the requirement for prospective participants to read, comprehend, and sign a complicated consent/HIPAA document while in labor will better respect their privacy considerations. An oral process will be considerably less intrusive, while respecting patient autonomy and addressing all other required elements of consent and HIPAA authorization.
- Patients will be free to read the educational materials, or not, as they see fit; similarly, they can choose to decline to answer any or all of the satisfaction-survey questions. The investigators do not anticipate that ongoing consent will become an issue.

#### **Non-English Speaking Subjects**

- Most prospective participants speak English. The majority of the remainder speak Spanish.
- PI [name] speaks some Spanish, and the educational website is available in Spanish. The consent process for these patients will occur in Spanish. Official UNM Hospital interpreters may be used to facilitate understanding.
- HRRC-approved Spanish-language documents will be used for patients who prefer to use Spanish.

